Acceptability will be assessed using a Participant Feedback questionnaire (See Feedback questionnaire attached).

2) Is the virtual SMART-3RP program effective for parents of children with learning disabilities?

a) Is there a significant difference in primary and secondary outcome measures between participants in the Immediate and Waitlist SMART-3RP groups at 3 mo. post enrollment?

We will use paired samples t-tests to compare within group differences on primary and secondary outcome measures from 3 mo. to baseline for the Immediate and Waitlist Groups. Primary outcome measures are the General Self-Efficacy Questionnaire (GSE), Current Experiences Scale (CES; from the Post Traumatic Growth Inventory), and the Visual Analogue 0-10 scales (VAS; measuring stress, distress, coping, and physical discomfort). Secondary outcome measures are: the Measure of Current Status-A (MOCS-A; to assess stress reactivity), Cognitive and Affective Mindfulness Scale-Revised (CAMS-R; to assess growth enhancement), and the Parental Stress Scale (PSS; to assess parental stress).

We will then use independent samples t-tests to compare the difference between the Immediate group's 3 months post enrollment and baseline assessment results with the

difference between the waitlist group's 3 months and baseline assessment results on primary and secondary outcome measures.

b) Among participants randomized to both conditions, will there be improvements in primary and secondary outcome measures from pre-post SMART-3RP (IG: assessments from baseline-3 mo.; WG: from 3-6 mo.)?

We will use paired samples t-tests to compare all primary and secondary assessments from pre-post SMART-3RP (for the IG, assessments are from baseline-3 mo.; for the WG, assessments are 3 mo. to 6 mo.).

c) Among the Immediate group only, will the changes from baseline to 3 months post enrollment (end of treatment) be sustained at 6 months post enrollment (3 months post treatment)?

We will use paired samples t-test to assess within-group differences in long-term outcomes. We will compare measures at the 6 months assessment to measures at the 3 months assessment for the Immediate group.

3) Will the virtual delivery SMART-3RP be effective in reducing participants' stress levels, measured by hair cortisol?

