STATISTICAL ANALYSIS PLAN

March 26, 2019

NCT# 02772432

Development of a Resiliency Training Program for Parents of Children With Specific

Learning Disabilities

Randomization

We asked participants for their daytime or evening time preferences prior to randomizing them to the intervention or control from November 2016 to September 2017, balancing for group size. Participants were randomized using a random plan generator, with 1:1 randomization.

Statistical Analyses

To assess study feasibility, we assessed enrollment, intervention session attendance (>6) and retention at time 2 (75% response; intervention group: end of treatment; wait-list control: 3-month post-enrollment) and time 3 (intervention group: 3-months post end-of treatment; wait-list control: end of treatment). Study completers and non-completers at time 2 were compared on baseline demographic characteristics using independent samples t-tests for continuous variables and Chi-square tests or Fisher's exact tests for categorical variables. To assess study acceptability, we reviewed participant self-report survey feedback (e.g., satisfaction with the number and length of intervention sessions, comfort level with group sessions, continued RR practice) and open-ended qualitative program feedback. To explore preliminary efficacy of the intervention to improve our proposed psychosocial outcomes, we first characterized the two randomized groups (intervention group and wait-list control) by baseline demographic factors and reviewed baseline psychosocial data for univariate distributions. We then used all available data to test between-group (intervention group versus wait-list control) differences in change scores from time 1 to time 2 (intervention group: end of treatment; wait-list control: 3-month post-enrollment) using independent samples t-tests. Using the intent-to-treat principle, we replicated the analysis using multiple imputation⁶⁶ (five imputed datasets) to address missingness at time 2.

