We followed our main preliminary efficacy analyses with a series of paired samples t-tests using all available data, to further characterize results. First, we evaluated changes in scores from time 1 to time 2 within each randomized group. To further explore intervention efficacy, we evaluated the combined change from pre- to post-intervention across intervention group condition participants (using time 1 to time 2 data) and wait-list control participants (using time 2 to time 3 data). Finally, we explored potential maintenance of intervention benefits by evaluating change in scores from time 2 to time 3 within the intervention group only. Additionally, to support a future larger scale trial, including identification of a potential moderator of intervention effects, we explored whether greater parenting stress at baseline was associated with greater changes in our proposed psychosocial outcomes among participants (before treatment and end of treatment) using Pearson correlations.

Running head: A VIRTUAL INTERVENTION PROMOTING RESILIENCY FOR PARENTS OF CHILDREN WITH LAD Analyses were conducted using IBM SPSS version 23.

Running head: A VIRTUAL INTERVENTION PROMOTING RESILIENCY FOR PARENTS OF CHILDREN WITH LAD

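### The moderator exploration correlates baseline parenting stress with change under treatment; without an arm-by-baseline interaction it can identify only a predictor of change

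*SAP*

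**What the plan says.** The last analysis in the SAP's Statistical Analyses section is introduced as serving a later study: "to support a future larger scale trial, including identification of a potential moderator of intervention effects". The method is that the investigators "explored whether greater parenting stress at baseline was associated with greater changes in our proposed psychosocial outcomes among participants". The window and statistic are given as "among participants (before treatment and end of treatment) using Pearson correlations". No arm term, interaction term or between-arm comparison of correlations is described.

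Three other places bear on this:

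- **Main efficacy test (SAP, Statistical Analyses).** It compares the randomised arms on "differences in change scores from time 1 to time 2", when the wait-list arm is still untreated. Baseline parenting stress does not enter.
- **Combined pre-to-post analysis (same section).** It uses time 1 to time 2 for the intervention arm, but for the other arm "wait-list control participants (using time 2 to time 3 data)". Both arms are therefore on treatment in their windows.
- **Outcome list (Protocol, section VI, question 2a).** The secondary outcomes end with "and the Parental Stress Scale (PSS; to assess parental stress)", so parenting stress is itself an outcome.

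The protocol contains no moderator aim. Its only regression-type model is the mixed model for hair cortisol.

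**The concern.** Moderation concerns how the between-arm difference varies with a baseline variable. A correlation computed over treated time contains no untreated comparison. It mixes any true moderation with natural course, general prognosis and regression to the mean. This is so whether the participants are both arms pooled or the intervention arm alone.

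Two details are also left open:

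1. The outcomes for this analysis are not listed. If PSS change is among them, a score may be correlated with its own change.
2. Baseline is not defined for wait-list participants, whose pre-treatment visit is time 2, not time 1.

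What is at stake is the design of the next trial. Read as moderation, a correlation could direct that trial towards high-stress parents when the data cannot say whether they benefit more than others.

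**Working it through.** The documents give no figure for this analysis, so there is none to reproduce.

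**Inputs from the documents.** About 70 participants (Protocol, section III, Recruitment), 1:1 allocation, and 75% response at time 2 (SAP). This gives 0.75 × 70 = 52.5, taken as 52, or 26 per arm.

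**Assumptions not in the documents.** Retest correlation rho of 0.5 to 0.9, equal variances at each visit, and two-sided p<0.05 as a yardstick (the SAP sets no threshold).

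**Step 1: the mismatch.** Suppose change in treated parents has slope -0.3 SD per SD of baseline stress with residual SD 0.75 (illustrative values). Then r = -0.3/√(0.3² + 0.75²) = -0.3/0.808 = -0.37. Moderation is the treated slope minus the untreated slope:

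| Wait-list slope, time 1 to time 2 | Moderation |
|---|---|
| -0.3 | 0 |
| 0 | -0.3 |
| -0.6 | +0.3 |

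The planned analysis returns -0.37 in all three cases. The mismatch itself depends on none of the assumed values.

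**Step 2: PSS against its own change.** With no effect and no moderation, corr(X0, X1 - X0) = -√((1 - rho)/2). The smallest |r| with p<0.05 at n=52 is 0.273. Simulated percentages of trials with p<0.05:

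| rho | Expected r | Pooled n=52, baseline = own pre-treatment score | Intervention arm only, n=26 | Pooled, wait-list baseline at time 1, random-intercept | Same, AR(1) |
|---|---|---|---|---|---|
| 0.5 | -0.50 | 97 | 77 | 44 | 80 |
| 0.7 | -0.39 | 83 | 52 | 28 | 69 |
| 0.8 | -0.32 | 64 | 36 | 20 | 55 |
| 0.9 | -0.22 | 36 | 20 | 12 | 33 |

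The expected r applies where baseline is the pre-treatment score (the two columns after it). In the last two columns, the wait-list arm contributes no artefact under a random-intercept model, because time 1 correlates equally with times 2 and 3. Under AR(1) it does contribute.

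**Step 3: other outcomes.** For an outcome Y, the expected correlation is (r[X1,Y2] - r[X1,Y1])/√(2(1 - rho)). It is zero, and the rejection rate is 5%, when the lagged and cross-sectional correlations are equal. If the cross-sectional correlation c is 0.3 to 0.5 and the lagged one is rho × c, the expression becomes -c√((1 - rho)/2). The rejection rate is then 8% to 43% at n=52 with baseline at each participant's own pre-treatment visit. With wait-list baseline at time 1 it is about 5% to 15% (random-intercept) or 7% to 26% (AR(1)).

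**Step 4: the interaction model under the same null.** An arm × baseline-PSS term on time 1 to time 2 data rejects in 4.8% to 5.1% of trials at 26 per arm.

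**Step 5: precision of the interaction.** The residual SD after adjusting for baseline is √(1 - rho²), which is 0.714 at rho 0.7. The standard error of the slope difference is about 0.714 × √(2/(26 - 3)) = 0.21, and the 95% half-width about 2.01 × 0.21 = 0.42 SD per SD. Power for a slope difference of 0.3 at 26 per arm is about 21%, 29%, 39% and 63% for rho 0.5, 0.7, 0.8 and 0.9. At 35 per arm and rho 0.7 it is 39%.

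**The case against.** The strongest reply concerns weight. The SAP presents this as exploratory, speaks only of a potential moderator, sets no decision rule and places it after the main tests. It can be read as screening a candidate for the larger trial to test properly. That limits the severity, but it does not turn a correlation under treatment into evidence, even preliminary evidence, about the arm difference.

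Second, the interaction has low power, would be repeated over as many as nine scores (GSE, CES, four VAS, MOCS-A, CAMS-R, PSS), and would be unplanned: the SAP is dated March 2019 and written in the past tense. All of this is true. It is why the estimate should carry an interval and no significance claim, and why relabelling alone is an acceptable fallback.

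Third, the unlisted outcomes can be taken to be those in the protocol. That is a fair reading, but it would include the PSS and so leaves the self-correlation problem open.

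Fourth, the largest percentages require that PSS change was analysed, the arms were pooled and wait-list baseline means time 2. If baseline means enrolment, the random-intercept figures fall to 44% to 12%. They are also sensitive to the correlation structure: AR(1) gives 80% to 33%. These figures are therefore conditional and are shown both ways. The mismatch between aim and method does not rest on them.

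**Conclusion.** The concern holds. The stated aim is "identification of a potential moderator of intervention effects", and the planned correlation cannot meet it under any reading of who the participants are. This follows from the definition of moderation and needs no assumed number.

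The regression-to-the-mean artefact is a secondary, conditional problem. It is potentially large if PSS is correlated with its own change (12% to 97% of null trials with p<0.05 across the cases examined). For other outcomes it is indirect and smaller, and it may be absent. These sizes rest on the assumed rho, 26 per arm and the 0.05 yardstick.

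No feasibility, acceptability or between-group result is affected, and the protocol has no moderator aim. This should be fixed, but it does not undermine the trial's main conclusions.

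**What to change.** **Preferred.** On the randomised time 1 to time 2 data, regress each time 2 outcome on arm, baseline outcome, baseline PSS and arm × baseline PSS. When PSS is the outcome, use arm, one baseline PSS term and its interaction with arm. Report each interaction estimate with its 95% CI, labelled exploratory and added after the original analyses, with no significance claims across outcomes.

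**If the correlations are kept.** Describe them as predictors of change, list the outcomes, omit PSS change, and state which visit is baseline for the wait-list arm.

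**Cost.** The preferred option needs revised SAP wording and one regression per outcome on data already collected. Its drawback is precision: with a half-width near 0.42 SD per SD (26 per arm, rho 0.7), it will often be inconclusive, and the report should say so. Relabelling needs no new modelling.
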